## **13 PROTOCOL VIOLATIONS**

A protocol violation occurs when the subject, investigator, or Sponsor fails to adhere to significant protocol requirements affecting the inclusion, exclusion, subject safety and primary endpoint criteria. Protocol violations for this study include, but are not limited to, the following:

- Failure to meet inclusion/exclusion criteria
- Use of a prohibited concomitant medication
- Failure to comply with Good Clinical Practice (GCP) guidelines.

The Sponsor will determine if a protocol violation will result in withdrawal of a subject.

When a protocol violation occurs, it will be discussed with the investigator and a Protocol Violation Form detailing the violation will be generated. This form will be signed by a Sponsor representative and the Investigator. A copy of the form will be filed in the site's regulatory binder and in the Sponsor's files.

## **14 DATA SAFETY MONITORING**

The Data Safety Monitoring Board (DSMB) will include one reproductive endocrinologist ([name]) and one hepatologist ([name], MD) who are UCSF faculty who are not directly involved in the study itself, but have expertise in use of spironolactone to treat elevated androgens in women, and expertise in liver disease respectively. This DSMB will review data relating to safety and efficacy, conduct and review interim analyses, and ensure the continued scientific validity and merit of the study. Further details regarding the timing and content of the interim reviews is included in the statistical section below.

## **15 STATISTICAL METHODS AND CONSIDERATIONS**

Prior to the analysis of the final study data, a detailed Statistical Analysis Plan (SAP) will be written describing all analyses that will be performed. The SAP will contain any modifications to the analysis plan described below.

### **15.1 Data Sets Analyzed**

All eligible patients will be included in the feasibility analyses because a key feature of this study is to determine the proportion of eligible patients that agree to participate. Only those randomized participants will be included in the analyses of secondary outcomes, though analyses will be conducted and presented separately as intention to treat, per protocol, and as treated, as the information gleaned from these different analytic approaches provides different, clinically relevant information.

All eligible patients who are randomized into the study and receive at least one dose of the study drug (the Safety Population) will be included in the safety analysis.

### **15.2 Demographic and Baseline Characteristics**

The following demographic variables at screening will be summarized by treatment group: race, ethnicity, age, body mass index, HOMA-IR, lipid levels, androgen levels, PCOS diagnosis, and menopausal status.

### **15.3 Analysis of Primary Endpoint**

Exact 95% confidence intervals for rates of agreement to participate, meeting eligibility criteria, and completing follow-up will be calculated using the binomial distribution.

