CONCOMMITANT MEDICATIONS- PROHIBITED	
 
- Androgen receptor antagonists (i.e. flutamide or flutamide) including current use of spironolactone
 
- Eplerenone as also blocks aldosterone receptor
 
- Drugs associated with fatty liver (i.e. amiodarone, methotrexate, systemic glucocorticoids, tamoxifen, anabolic steroids, valproic acid)
 

EFFICACY EVALUATIONS	
As a pilot trial this study is not powered to detect an effect of spironolactone on NASH progression in women. The primary goal of the study is rather to evaluate the feasibility and tolerability of the study intervention and outcome measures in women with NASH while also exploring the mechanisms by which blocking testosterone receptors may alter NASH severity or associated metabolic comorbidities leading to NASH. If the intervention is deemed to be feasible, and we detect a signal that spironolactone may alter these biologic processes, then these data would be used to support a larger trial aimed at assessing the efficacy of spironolactone or other related androgen modulating medication on the treatment of NASH in women.

PRIMARY ENDPOINTS	
Feasibility endpoints:
 
 
• Adherence and acceptability of spironolactone in women with NASH
 
• Adherence and acceptability of study outcome measures (MRI and optional EOT biopsy)
 
 
Determine the range of NASH on baseline biopsy to inform inclusion criteria for larger trials

SECONDARY ENDPOINTS	
 
• Biochemical endpoints: serum lipids, HOMA-IR, liver enzymes
 
• Radiologic endpoints: liver fat quantity, visceral fat volume, liver inflammation, liver scarring
 
• Histologic endpoints: Change in NAFLD Activity Score (NAS)
 
• Expression of androgen receptors in the liver and circulating hormone levels.
 

SAFETY EVALUATIONS	
Spironolactone is an old, commonly used medication to treat symptoms of high androgens in women therefore has a longstanding favorable side effect profile. Change in clinical safety labs and in person review of potential side effects will be assessed at each study visit. Incidence of adverse events will be collected.

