PLANNED INTERIM ANALYSES	The Data Safety Monitoring Board (DSMB) will review the progress of the study and perform an interim review of the safety data after the first 10 participants have completed 3 months of spironolactone, or at any time that a comprehensive review of safety is felt to be necessary. The committee will provide recommendations to [name] whether the nature, frequency, and severity of adverse effects associated with study treatment warrant the early termination of the study in the best interests of the participants, whether the study should continue as planned, or the study should continue with modifications. The DSMB may also provide recommendations as needed regarding study design, or changes to study conduct.
STATISTICS Primary Analysis Plan	The focus of the pilot trial will be feasibility testing and obtaining preliminary assessments of the effects of spironolactone. Exact 95% confidence intervals for rates of agreement to participate, meeting eligibility criteria, completing follow-up will be calculated using the binomial distribution. Between-group analyses will be performed according to the intention-to-treat principle. We will attempt to collect complete follow-up data on every randomized participant, regardless of adherence to treatment. As randomization in this small sample may not result in the perfect balance of relevant biological variables (e.g., age or weight between groups) we will perform analyses adjusting for any of these that are substantially imbalanced. A planned interim analysis will be conducted after the first 10 participants (25%) have completed 3 months of spironolactone. Interim results will provide useful preliminary safety and feasibility data.
Rationale for Number of Subjects	The sample size of 30 was determined based on budget and feasibility within a 4-year grant timeline. The sample size is also reasonable for pilot trial, and will allow us to estimate effects and feasibility with reasonable precision.

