### 2.1 Risk / Benefit Assessment

The risks involved in this pilot clinical trial are reasonable in relation to the anticipated benefits to the participant and to society, including understanding the role of androgens in the pathway of NASH and associated metabolic conditions, which may provide preliminary feasibility and biologic data to support larger trials to develop hormone targeted therapy to treat NASH in women.

The specific risks and methods for mitigating these are as follows:

**1) Privacy breach:** Eligible participants will be initially contacted in person during clinic visits by the principal investigator or research assistant to ascertain interest in study participation. If participants are interested and come for a screening visit, they will be sent the informed consent form prior to the visit to allow ample time to review. At the study visit, the PI or study coordinator will read aloud the consent form with the

participant, describing the information we are seeking, procedures and indications, the voluntary nature of the study, the risks and benefits, and the ability to refuse or withdraw at any time without adverse consequences. The participant's understanding of the study and its requirements will be confirmed, and any questions they have will be addressed prior to signing consent. A copy of the consent will be retained for the participant and the participant's file, which is kept in a locked cabinet in a locked office.

There is a risk of loss of confidentiality for subjects in the study, despite maximal measures to minimize this risk. Maximal safeguards to maintain participants' confidentiality will be employed, including: 1) unique study identification numbers on all forms and specimens 2) maintaining identifiers in a password-protected database, and 3) restricting access to the password protected database and locked study documents to essential study personnel.

**2) Risks of frequent phlebotomy:** The risks of routine blood drawing are rare but can include pain, bleeding, bruising at the site, anemia, dizziness, and very rarely an infection at the site. Only trained phlebotomists will perform blood draws. Phlebotomy risks will be minimized by the use of trained personnel and application of pressure after the blood draw. Should any adverse event occur, medical attention by a licensed physician will be provided immediately.

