#### **3.2 Secondary Objectives**

- To examine the effect of spironolactone on features of NASH on MRE and MRI-PDFF
- To examine the effect of spironolactone on features of NASH on liver biopsy
- To examine the effect of spironolactone on metabolic parameters that contribute to NASH progression
- To examine the effect of spironolactone on sex hormone levels and androgen receptor expression in liver tissue

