## 5 CRITERIA FOR EVALUATION

### 5.1 Primary Endpoints

This is a pilot clinical trial that is largely feasibility focused. The primary goal is to establish if spironolactone is feasible in women with NASH, and if our study outcome measures are reasonable. The feasibility endpoints will include:

- Rates (and reasons) for the following: a) % women that decline/women contacted for study inclusion (i.e. need for a second liver biopsy, concern regarding randomization to placebo) b) % women enrolled/women screened (i.e. exclusion criteria too narrow), c) study dropout (i.e. medication side effects, too frequent study visits, and/or phlebotomy)
- Describe the range of NASH histology seen on biopsy in consideration of designing a future clinical trial.
- Radiologic endpoints: liver fat quantity, visceral fat volume, liver inflammation, liver scarring. These endpoints will be examined because they offer a non invasive way of assessing visceral fat, another metabolic factor that may be altered by testosterone blockade, as well as other non invasive measures of assessing liver fat and inflammation that could potentially allow for avoidance of liver biopsy in future studies.

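### The Safety Population can omit a dosed woman found ineligible, adherence and MRI/biopsy uptake (primary in the synopsis) have no planned summary, and the radiologic endpoints have two statuses

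*Combined protocol and SAP*

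**What the plan says.** **Primary endpoints.** The synopsis lists "Adherence and acceptability of spironolactone in women with NASH" and "Adherence and acceptability of study outcome measures (MRI and optional EOT biopsy"), together with the range of NASH on baseline biopsy. Section 5.1 gives another list: refusal, expressed as "women that decline/women contacted for study inclusion"; enrolment among women screened; dropout; the range of histology; and the radiologic endpoints.

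**Analyses.** The whole of section 15.3 is: "Exact 95% confidence intervals for rates of agreement to participate, meeting eligibility criteria, and completing follow-up will be calculated using the binomial distribution". Section 15.4 plans regressions for the effect of spironolactone, a tolerability summary and adverse event tables by arm.

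**Imaging.** Section 5.1 places under its primary heading: "Radiologic endpoints: liver fat quantity, visceral fat volume, liver inflammation, liver scarring. These endpoints will be examined because they offer" a non-invasive route that might spare biopsies in later studies. Section 5.2 does not mention imaging. The synopsis lists the same endpoints as secondary, and section 3.2 makes imaging a secondary objective: "To examine the effect of spironolactone on features of NASH on MRE and MRI-PDFF".

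**Analysis sets.** Section 15.1 assigns eligible patients to the feasibility analyses. It defines the Safety Population by three conditions: eligible, randomized and dosed at least once. Section 13 names failure to meet the entry criteria as a protocol violation and lets the sponsor decide whether withdrawal follows.

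**The concern.** Feasibility is the purpose of this pilot, and section 2 says that its results are to feed a larger trial. A woman can complete follow-up while taking few capsules, or attend every visit and refuse the second biopsy. Completion of follow-up therefore does not answer the two questions that the synopsis calls primary: do women take the drug, and do they accept the outcome measures?

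The safety point is separate and simpler. The reason for a safety set is exposure. A woman found after dosing to have breached, say, the renal or potassium exclusion in section 6.3 is one whose safety data matter most, yet the stated rule removes her.

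The two statuses of the imaging endpoints leave it unclear which results will be presented as primary. If section 5.1 governs, section 15.3 contains no analysis for them.

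**Working it through.** The plan gives no precision or adherence figure to reproduce. Section 15.6 sets the sample size of 30 by budget and timeline, and 2:1 allocation gives 30 × 2/3 = 20 and 30 × 1/3 = 10, as the synopsis states. The check is mainly a comparison of texts.

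**1. Where each item appears**

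| Item | Synopsis | 5.1 (primary) | 5.2 (secondary) | 15.3 / 15.4 | Data collected |
|---|---|---|---|---|---|
| Drug adherence | Primary | Absent | Absent | No summary | Capsule counts: 5.3, 8.8, 10.3, 10.4 |
| End-of-treatment MRI uptake | Primary | No rate | Absent | No summary | 9.4, 10.4 |
| Optional biopsy uptake | Primary | No rate; second biopsy only as an example of a reason to decline | Absent | No summary | 9.3, 10.4 |
| Radiologic endpoints | Secondary | Listed | Absent | Not in 15.3; regressions in 15.4 as secondary | 9.4, 10.4 |

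Reasons for declining and dropping out (5.1), completion of follow-up (15.3) and the tolerability summary (15.4) bear on acceptability, but they are only partial proxies. The 5.1 and 15.3 rates otherwise largely mirror each other: decline against agreement, dropout against completion. The mismatch is mainly between the synopsis and the body of the protocol.

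**2. Safety Population**

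Section 15.1 requires eligible *and* randomized *and* dosed. Section 13 admits that a woman may be in the trial without meeting the criteria. Such a woman, once dosed, satisfies the last two conditions and fails the first. Section 11.2.1 documents her serious adverse events from consent onward, but that does not put her in the safety tables. At the planned sizes, one woman is 1/30 = 3.3% of the trial, 1/20 = 5% of the spironolactone arm or 1/10 = 10% of the placebo arm. The documents give no basis for saying how likely this is.

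**3. What the missing proportions would show**

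For x of n, the exact 95% limits are: lower = 2.5% quantile of Beta(x, n − x + 1); upper = 97.5% quantile of Beta(x + 1, n − x). The observed counts are assumptions.

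- All women: 15/30 gives 31.3–68.7%; 24/30 gives 61.4–92.3%; 27/30 gives 73.5–97.9%.
- Spironolactone: 16/20 gives 56.3–94.3%.
- Placebo: 8/10 gives 44.4–97.5%.

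These show expected precision, not the size of the defect.

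**4. Denominators (minor)**

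- *Eligible* has two uses. Section 2.1 applies it before screening: "Eligible participants will be initially contacted in person during clinic visits". Section 6.1 applies it to women who meet the criteria. Section 15.1 does not say which it means.
- Dropout in 5.1 has no stated denominator. The synopsis points to all randomized women: "We will attempt to collect complete follow-up data on every randomized participant, regardless of adherence to treatment".
- Section 8.1 does not replace dropouts in the randomization scheme, section 8.4 replaces women randomized but not treated, and section 12.3 replaces women who withdraw from treatment. None says whether a replaced woman still counts in the completion rate.

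**The case against.** The synopsis is part of the protocol, so naming adherence as primary is itself a commitment to report it. Section 15 also promises a detailed SAP. This stands in part. A reader might infer that nothing obliges the team to report adherence, and that goes too far. What is missing is the measure, the denominator and the method. The later SAP would have to choose between texts that disagree.

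Section 4.1 admits only women who meet all criteria, so *eligible* in the safety definition may be loose wording. That is plausible, but it argues for deleting the word.

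Section 5.1 justifies imaging as a possible substitute for biopsy, which is a feasibility reason, while section 3.2 concerns treatment effect. This softens the conflict without removing it: the same endpoints still sit under different headings. Nor is 5.1 the lone exception, because 5.2 omits imaging too, so the body is consistent with itself and at odds with the synopsis and the objectives.

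A reader might also infer that the eligibility rate must be 100% because the feasibility set is confined to eligible women. The documents do not support this. Section 15.1 explains that the set serves the proportion of eligible patients who agree, and 5.1 gives contacted and screened women as its own denominators. What remains is an undefined term.

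Finally, a reader might compute a large gap in the completion rate by assuming that withdrawn women are replaced and then removed from the denominator. No dropout rate is given. The synopsis seeks follow-up on every randomized woman, and section 12.1 brings those who stop treatment in for an end-of-treatment visit. The replacement statements may also concern different cases. No size should be attached to this.

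**Conclusion.** Three points stand on the text and should be settled before the final analysis. First, the Safety Population as worded can exclude an exposed woman; each exclusion is 5% of the planned spironolactone arm or 10% of placebo, with frequency unknown. Second, drug adherence and uptake of the end-of-treatment MRI and biopsy are primary in the synopsis and have no summary in 5.1, 15.3 or 15.4. Third, the radiologic endpoints have two statuses. The undefined term in 15.1 and the replacement statements call for clarification only. The safety point rests on a literal reading of 15.1. The intervals rest on assumed counts at the planned arm sizes.

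**What to change.** 1. **Section 15.1:** define the Safety Population as all randomized women who took at least one dose, deleting *eligible*.
2. **Sections 5.1 and 15.3:** add a pill-count adherence summary and the proportions of all randomized women who complete the end-of-treatment MRI and who accept the biopsy. Give exact 95% intervals for the proportions overall, and by-arm intervals as descriptive only. For women who extend, state whether Month 6 or Month 12 counts: section 9.4 scans them at both, and section 10.6 moves their biopsy to Month 12.
3. **Synopsis, 5.1 and 5.2:** the sponsor gives the radiologic endpoints one status. If they stay primary, add their analysis to 15.3; if secondary, list them in 5.2.
4. **Minor, 15.1:** give *eligible* one meaning for the agreement rate. Eligibility as judged at first contact is the workable choice, because women who decline then are never screened. Keep contacted and screened women as the 5.1 denominators, and use all randomized women for dropout and completion. Reconcile the replacement statements in 8.1, 8.4 and 12.3, and say that replaced women remain in the randomized denominator.

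The cost is wording in these sections and a few tabulations of data already planned, with no new visits or procedures. The by-arm intervals will be too wide for comparison between arms.

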### **3 STUDY OBJECTIVES**

#### **3.1 Primary Objective**

To establish the feasibility and tolerability of the intervention and study outcomes measures.

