### **15.4 Analysis of Secondary Endpoints**

Logistic regression will be used to assess the association of spironolactone with each dichotomous outcome, and ordinal logistic or linear regression used to evaluate the association of spironolactone with change in either ordered categories or continuous measures, where appropriate.

Safety and tolerability data will be summarized by treatment group.

Adverse event rates will be coded by body system and MedDRA classification term. Adverse events will be tabulated by treatment group and will include the number of patients for whom the event occurred, the rate of occurrence, and the severity and relationship to study drug.

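### The primary analysis in Section 15.3 contains no rate of adherence or of staying on study drug, so it cannot answer the tolerability part of the primary objective

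*Combined protocol and SAP*

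**What the plan says.** The primary objective (Section 3.1) is "To establish the feasibility and tolerability of the intervention and study outcomes measures". The Synopsis lists as a primary endpoint "Adherence and acceptability of spironolactone in women with NASH". Section 5.1 puts among the feasibility endpoints, with rates and reasons, "study dropout (i.e. medication side effects, too frequent study visits, and/or phlebotomy".

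The primary analysis in Section 15.3 is one sentence: "Exact 95% confidence intervals for rates of agreement to participate, meeting eligibility criteria, and completing follow-up will be calculated using the binomial distribution". The Synopsis repeats it. Neither place defines completion of follow-up or mentions treatment arm.

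On what happens after a woman stops the drug:
- Synopsis, Primary Analysis Plan: "We will attempt to collect complete follow-up data on every randomized participant, regardless of adherence to treatment".
- Section 11.3: women temporarily off drug keep to the normal visit schedule.
- Section 12.1: women who discontinue treatment are called in early for an End of Treatment visit. Whether that visit completes follow-up is not stated.

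Section 15.4, under secondary endpoints, says: "Safety and tolerability data will be summarized by treatment group". It adds adverse-event tables by arm. Pill counts are taken at the treatment visits (Sections 10.3 and 10.4), but Section 15 contains no analysis of them or of stopping study drug.

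**The concern.** A tolerability objective asks how many women given spironolactone could keep taking it. Of the three rates in Section 15.3, agreement and eligibility are settled before any capsule is taken, so only completion of follow-up could bear on the question. That rate measures attendance. The plan deliberately separates attendance from taking the drug. This is right for intention-to-treat analysis, but it makes attendance a poor stand-in for tolerability.

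The pilot is meant to supply feasibility results for a larger trial (Synopsis, Efficacy Evaluations; Section 2). If the primary result says only that women came to their visits, the planners of that trial will not have the quantity they need most: the proportion still on spironolactone at Month 6, with its uncertainty. Because completion is undefined, the same woman could also be scored either way after the data are seen.

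**Working it through.** **1. The plan's own figure.** The only relevant figure is the sample size: 30 at 2:1, so 30 × 2/3 = 20 on spironolactone and 30 × 1/3 = 10 on placebo. This agrees with the Synopsis. Section 15.6 bases the 30 on budget and feasibility and gives no expected rate or interval width, so there is nothing further to reproduce.

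**2. Primary aims against primary analysis.**

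| Stated aim | Rate in Section 15.3 |
|---|---|
| Willingness to join | Agreement to participate |
| Breadth of eligibility criteria | Meeting eligibility criteria |
| Study dropout | Completing follow-up (undefined, arm not stated) |
| Tolerability of the intervention | None |
| Adherence to spironolactone | None |

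**3. Interval method.** Section 15.3 specifies "Exact 95% confidence intervals", taken here as two-sided Clopper-Pearson. For x events in n, the lower limit is the 2.5% quantile of Beta(x, n − x + 1) and the upper limit is the 97.5% quantile of Beta(x + 1, n − x). For x = n the lower limit is 0.025^(1/n) and the upper limit is 100%. For 30/30 the lower limit is 0.025^(1/30) = 88.4%.

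**4. Attendance against staying on drug.** The documents give no stopping rate, so these counts are assumptions shown over a range. All 30 women attend, and attendance is taken to count as completion.

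| Stop spironolactone | Completion of follow-up | Still on spironolactone (exact 95% CI) |
|---|---|---|
| 0 of 20 | 30/30 = 100% (88.4 to 100) | 20/20 = 100% (83.2 to 100) |
| 2 of 20 | 30/30 = 100% (88.4 to 100) | 18/20 = 90% (68.3 to 98.8) |
| 4 of 20 | 30/30 = 100% (88.4 to 100) | 16/20 = 80% (56.3 to 94.3) |
| 6 of 20 | 30/30 = 100% (88.4 to 100) | 14/20 = 70% (45.7 to 88.1) |
| 8 of 20 | 30/30 = 100% (88.4 to 100) | 12/20 = 60% (36.1 to 80.9) |

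For 6 of 20, the proportion stopping is 30%, with limits 100 − 88.1 = 11.9% and 100 − 45.7 = 54.3%. The middle column does not move.

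**5. If the rate were reported for both arms together.** A combined 24/30 = 80% (61.4 to 92.3) fits spironolactone 14/20 = 70% (45.7 to 88.1) with placebo 10/10. It fits equally well spironolactone 20/20 = 100% (83.2 to 100) with placebo 4/10 = 40% (12.2 to 73.8). The combined figure cannot tell these apart.

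**6. What by-arm reporting can do.** At 20 against 10, power to separate stopping rates of 30% and 10% is about 19%, and for 40% and 10% about 37% (normal approximation, two-sided 5%). By-arm rates are therefore estimates, not the basis of a test.

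**7. The denominator.** Section 15.1 states: "All eligible patients will be included in the feasibility analyses because a key feature of this study is to determine the proportion of eligible patients". This set includes women who were never randomized, so it cannot serve for completion. Section 8.1 says dropouts are not replaced in the randomization scheme; Section 12.3 says women who withdraw from treatment are replaced. If 6 of 20 stopped, and six replacements all entered the spironolactone arm and stayed on drug, the proportion stopping would be 6/26 = 23.1% instead of 6/20 = 30%. If women who were replaced left the denominator, it would be 0/20.

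**The case against.** A reader might infer that Section 15.3 pools the arms. It does not say so. It is silent on arm, and for agreement and eligibility no arm exists. Sections 15.2 and 15.4 do specify reporting by treatment group, which makes pooling a natural reading of the silence, but it remains an inference.

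A reader might also infer that a woman who has stopped the drug counts as completing follow-up. That too is unstated. The Synopsis promises an attempt to collect data and does not define success. Section 11.3 covers only temporary stopping, and Section 12.1 leaves the permanent stopper unclassified. Section 5.1 names side effects as a reason for dropout, so some women who stop would presumably appear there. The 30/30 rows show what the wording permits, not what it dictates.

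Section 15.4 already plans a by-arm summary of tolerability as well as adverse events, so it would be wrong to say the plan ignores tolerability by arm. That point stands. But the summary sits under the secondary endpoints and names no rate, time point or interval. An adverse-event table does not show how many women came off drug.

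Section 2.1 expects side effects other than increased urination in under 1% at the study dose, so stopping for adverse events may be rare. That would narrow the gap in practice. Even so, a rate with its interval is informative: 0 of 20 stopping has an upper limit of 100 − 83.2 = 16.8%.

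Overall dropout remains a legitimate feasibility measure, since visits and phlebotomy burden both arms. Section 15 also defers detail to a later SAP, which is where the repair can be made, but it does not supply the missing rates.

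**Conclusion.** The concern holds in this form: the primary analysis omits adherence and staying on drug although both belong to the primary aims. Its one post-randomization rate is undefined, has no stated arm, and can be high while many women on spironolactone have stopped. The documents do not establish that the arms are pooled or that women off drug are scored as completers; the fault is that both are left open.

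On size, with full attendance counted as completion, the reported rate is 100% (88.4 to 100) while 60% to 90% of the spironolactone arm is still on drug, for 8 down to 2 women stopping. These counts are assumptions, as is the two-sided exact interval. The finding that Section 15.3 has no on-treatment or adherence rate depends on neither.

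**What to change.** In Section 15.3 and the SAP:
1. Define completion of follow-up and completion of study treatment separately, and say how a woman seen at an early End of Treatment visit is classified for each.
2. Report by arm, among all randomized women: both completion rates; permanent discontinuation of study drug by Month 6, for any reason and for an adverse event; and pill-count adherence. Give exact 95% intervals for the proportions.
3. Show any between-arm difference descriptively, not as a test.
4. Keep agreement and eligibility as single overall rates, and keep overall dropout as an additional feasibility figure.
5. Reconcile Sections 8.1 and 12.3 on replacement before the denominator is fixed.

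The cost is mainly wording. By-arm intervals are wider: for 80%, 56.3 to 94.3 with 16/20 against 61.4 to 92.3 with 24/30. One case report form field may also be needed for the reason for stopping drug. Section 12.1 lists possible reasons without saying that they are recorded; the recording rule in Section 12.2 covers withdrawal from the study.
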